5.2 Dose Interruptions/Withholding

Study treatment, including APR-246, venetoclax, and/or rituximab, may be withheld from a patient based on the Investigator's decision in the event of intercurrent illness, AE, administrative reasons, or other reasons. If the patient's condition subsequently improves, or the situation that resulted in withholding study drug rectifies itself, the Investigator may resume dosing as soon as possible, unless the delay is more than 4 weeks. For study treatments held longer than 4 weeks, the Investigator should consult with the Medical Monitor before study treatments are resumed.

Dose management guidelines in [Table 5](#) should be followed for each occurrence of a grade ≥ 3 hematologic toxicity or those in [Table 6](#) for non-hematologic toxicity.

Table 5. Dose management guidelines for new onset hematologic toxicities

Toxicity	Occurrence	APR-246	Venetoclax	Rituximab
Grade 3 hematologic toxicity with fever and/or infection; or grade 4 hematologic toxicity	1 st occurrence • Hold all study treatments until blood count(s) return to baseline or grade ≤1 and fever and/or infection resolve if present. Treat promptly.	
 Consider reducing APR-246 by one dose level from starting dose for all future cycles of treatment if toxicity does not resolve to grade ≤1 within 7 days from onset date despite maximal medical intervention(s). If unable to reduce APR-246 dose, discuss with study Medical Monitor before resuming or discontinuing treatment. Initiate or reassess prophylaxis measures. Refer to Section 5.3.2.2 for supportive management guidelines specific to infection prophylaxis and neutropenia. 	
 Refer to Section 5.3.3.1 for venetoclax dose modification guidelines. 	
 Resume rituximab at same dose level once event resolves to baseline or grade ≤1, except in case of serious infection. For patients diagnosed with a serious grade ≥3 infection, rituximab should be permanently discontinued.

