	2 nd occurrence • Hold all study treatments until blood count(s) return to baseline or Grade ≤1 and fever and/or infection resolve if present. Treat promptly.	
 Consider reducing APR-246 by one dose level from current dose for all future cycles of treatment if the toxicity does not resolve to grade ≤1 within 7 days from onset despite maximal medical intervention(s). If unable to reduce APR-246 dose, discuss with study Medical Monitor before resuming or discontinuing treatment. Initiate or reassess prophylaxis measures. Refer to Section 5.3.2.2 for supportive management guidelines specific to infection prophylaxis and neutropenia. 	
 Refer to Section 5.3.3.1 for venetoclax dose modification guidelines. 	
 Reduce rituximab dose from 500 mg/m² to 375 mg/m². If unable to reduce dose of rituximab, discuss with study Medical Monitor before resuming treatment. For patients diagnosed with a serious grade ≥3 infection, rituximab should be permanently discontinued.
	3 rd occurrence • Hold all study treatments until blood	
 Consult with study medical monitor to determine if further dose modifications of study treatment(s) are medically necessary or if study treatment(s) should be discontinued. 		

	
count(s) return to baseline or grade ≤1 and fever and/or infection resolve if present. Treat promptly.
	
Assess current prophylaxis measures being administered and adjust treatment plan as clinically indicated. Refer to Section 5.3.2.2 for supportive management guidelines specific to infection prophylaxis and neutropenia.
--	---	--

Administration of supportive measures such as G-CSF, platelet or blood transfusions, and/or antimicrobial therapy should be considered as clinically indicated.

Actions noted in table above for rituximab are specific to toxicities occurring during Cycles 2 through 7. Rituximab may be reduced by one dose level, from 500 mg/m² to 375 mg/m², when clinically indicated. Please consult with study Medical Monitor to discuss dose modification(s) for rituximab.

Patients experiencing 3 occurrences of the same toxicity should be discussed with the study Medical Monitor before study treatments are resumed.

Dose management guidelines for non-hematologic toxicities are provided below in [Table 6](#).

Table 6. Dose management guidelines for Grade 3 or 4 non-hematologic toxicities

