Occurrence	APR-246	Venetoclax	Rituximab
1 st occurrence • Hold all study treatments until toxicity returns to baseline or grade ≤1. Treat promptly.	
Consider reducing APR-246 by one dose level from current dose for all future cycles of treatment if toxicity does not resolve to grade ≤1 within 7 days from onset date despite maximal medical intervention(s).If unable to reduce APR-246 dose, discuss with study Medical Monitor before resuming or discontinuing treatment.	Refer to Section 5.3.3.1 for venetoclax dose modification guidelines.	Resume rituximab at same dose level once event resolves to baseline or grade ≤1, except in case of serious infection. For patients diagnosed with a serious grade ≥3 infection, rituximab should be permanently discontinued.
2 nd occurrence • Hold all study treatments until toxicity returns to baseline or grade ≤1	
Consider reducing APR-246 by one dose level from starting dose for all future cycles of treatment.	Refer to Section 5.3.3.1 for venetoclax dose modification guidelines.	Reduce rituximab dose from 500 mg/m ² to 375 mg/m ² . If unable to reduce rituximab, discuss with study Medical Monitor before resuming or discontinuing rituximab. For patients diagnosed with serious grade ≥3 infection, rituximab should be permanently discontinued.
3 rd occurrence • Hold all study treatments until toxicity returns to baseline or grade ≤1. Treat promptly.	
Consult with study medical monitor to determine if further dose modifications of study treatment(s) are medically necessary or if study treatment(s) should be discontinued.		

Actions noted in table above for rituximab are specific to toxicities occurring during Cycles 2 through 7. Rituximab may be reduced by one dose level, from 500 mg/m² to 375 mg/m², when clinically indicated. Please consult with study Medical Monitor to discuss dose modification(s) for rituximab.

Treatment may be discontinued if a TEAE has not improved (to an acceptable grade) or resolved after ≥ 4 weeks, at the discretion of the Investigator. Please consult study Medical Monitor if this situation occurs.

Patients experiencing 3 occurrences of the same toxicity should be discussed with the study Medical Monitor before study treatments are resumed.

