5.3.4.2 Severe Mucocutaneous Reactions

Mucocutaneous reactions, some with fatal outcome, can occur in patients treated with rituximab. These reactions include paraneoplastic pemphigus, Stevens-Johnson syndrome, lichenoid dermatitis, vesiculobullous dermatitis, and toxic epidermal necrolysis. The onset of these reactions has been variable and includes reports with onset on the first day of rituximab exposure. Discontinue rituximab in patients who experience a severe mucocutaneous reaction. The safety of re-administration of rituximab to patients with severe mucocutaneous reactions has not been determined.

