5.3.4.3 Hepatitis B Virus Reactivation

Hepatitis B virus (HBV) reactivation, in some cases resulting in fulminant hepatitis, hepatic failure and death, can occur in patients treated with drugs classified as CD20-directed cytolytic antibodies, including rituximab.

HBV reactivation is defined as an abrupt increase in HBV replication manifesting as a rapid increase in serum HBV DNA levels or detection of hepatitis B surface antigen (HBsAg) in a person who was previously HBsAg negative and anti-HBc positive. Reactivation of HBV replication is often followed by hepatitis, i.e., increase in transaminase levels. In severe cases increase in bilirubin levels, liver failure, and death can occur.

Monitor patients with evidence of current or prior HBV infection for clinical and laboratory signs of hepatitis or HBV reactivation during and for several months following rituximab therapy. HBV reactivation has been reported up to 24 months following completion of rituximab therapy.

In patients who develop reactivation of HBV while on rituximab, immediately discontinue rituximab and any concomitant chemotherapy, and institute appropriate treatment. Insufficient data exist regarding the safety of resuming rituximab treatment in patients who develop HBV reactivation.

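### Table 6 has rituximab resumed after resolved grade 3–4 events that Section 5.3.4 may require to end it, most clearly a severe mucocutaneous reaction, and no text says which rule governs

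*Combined protocol and SAP*

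**What the plan says.** Section 5.2 tells sites to follow Table 6 for non-hematologic toxicity. The title sets the scope, with no event type left out: "Table 6. Dose management guidelines for Grade 3 or 4 non-hematologic toxicities".

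The rituximab column works as follows.

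- **First occurrence.** All study treatments are held, then: "Resume rituximab at same dose level once event resolves to baseline or grade ≤1, except in case of serious infection". One permanent stop follows: "For patients diagnosed with a serious grade ≥3 infection, rituximab should be permanently discontinued".
- **Second occurrence.** Rituximab is reduced from 500 to 375 mg/m², with the same infection stop.
- **Third occurrence.** The site consults the Medical Monitor.

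Section 5.3.4 gives rituximab-specific rules.

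- **5.3.4.2, severe mucocutaneous reactions:** "Discontinue rituximab in patients who experience a severe mucocutaneous reaction", followed by "The safety of re-administration of rituximab to patients with severe mucocutaneous reactions has not been determined".
- **5.3.4.3, hepatitis B reactivation:** "immediately discontinue rituximab and any concomitant chemotherapy, and institute appropriate treatment".
- **5.3.4.4, PML:** rituximab is discontinued.
- **5.3.4.5, cardiac:** infusions are discontinued for serious or life-threatening arrhythmias.
- **5.3.4.1, infusion-related reactions:** rituximab is stopped temporarily or permanently, depending on severity and the interventions needed.

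The venetoclax column of Table 6 points to Section 5.3.3.1, which points back to Section 5.2 for overlapping toxicities. The rituximab column has no pointer to Section 5.3.4, and Section 5.3.4 has none to Section 5.2.

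**The concern.** A severe mucocutaneous reaction graded 3 or 4 is a non-hematologic toxicity, so it falls under both texts. After it resolves, Table 6 gives the next dose and Section 5.3.4.2 does not. Section 5.3.4.2 names Stevens-Johnson syndrome and toxic epidermal necrolysis among these reactions and says that some are fatal.

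The table invites the unsafe reading because it states an exception of its own, and a named exception can be taken as the complete list. The verbs add to this. Table 6 says permanently for infection, and Section 5.3.4.1 distinguishes temporary from permanent discontinuation, but Section 5.3.4.2 says only to discontinue. A site could therefore stop the drug, wait for resolution and resume under Table 6, believing that it had followed both texts.

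**Working it through.** There is no stated figure to reproduce. The check sets the texts side by side and then places the rituximab infusions against the DLT period.

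**1. Does Table 6's exception cover each rule in Section 5.3.4?**

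| Rule | Action in 5.3.4 | Readable as serious infection? | Table 6, first occurrence, if grade 3–4 and resolved |
|---|---|---|---|
| 5.3.4.2 mucocutaneous | Discontinue | No | Resume, same dose: conflict |
| 5.3.4.3 HBV reactivation | Discontinue at once | Yes (viral) | Covered on that reading |
| 5.3.4.4 PML | Discontinue | Yes (viral) | Covered on that reading |
| 5.3.4.5 arrhythmia | Discontinue infusions | No | Resume, same dose: conflict unless only the current infusion is meant |
| 5.3.4.1 infusion reaction | Temporary or permanent stop | No | Resume, same dose: conflict where the stop should be permanent |

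The mucocutaneous rule is the clearest conflict. The last two rows depend on interpretation.

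**2. Is there a tie-breaker?** None is written. The nearest is the note under Table 6: "Please consult with study Medical Monitor to discuss dose modification(s) for rituximab". Resuming at the same dose is not clearly a dose modification. Section 5.2 also says: "For study treatments held longer than 4 weeks, the Investigator should consult with the Medical Monitor before study treatments are resumed". Rituximab is scheduled every 28 days, which is 4 weeks, so a reaction that resolves by the next planned dose need not reach that rule.

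**3. When would the conflict arise?** Inputs: a 7-day lead-in, a 35-day Cycle 1 and 28-day later cycles (Section 4.1); rituximab on Day 2 of Cycles 2–7, at 375 mg/m² in Cycle 2 and 500 mg/m² afterwards (Section 5.1.3).

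- Cycle 2, Day 2 = 7 + 35 + 2 = study day 44. Adding 28 each time gives days 72, 100, 128, 156 and 184.
- Section 5.1.4 puts the end of the DLT period at up to day 91 (7 + 84). Section 4.1 runs it to the end of Cycle 3: 7 + 35 + 28 + 28 = day 98.
- Under either end, 2 of the 6 infusions (days 44 and 72) fall inside the DLT period and 4 fall outside.
- Infusions remaining after Cycle c = 7 − c: 5, 4, 3, 2, 1 and 0 for Cycles 2 to 7.

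First reactions after the Cycle 4, 5 or 6 infusion are the least guarded. They come after the DLT period and leave 3, 2 or 1 infusions, all planned at 500 mg/m². Under Section 5.3.4.2 none of these is given. Under Table 6 the next is given at the same dose. After Cycle 3, 4 infusions remain and the infusion lies within the DLT period. After Cycle 2, 5 remain, and the table's same-dose instruction does not fit the planned step from 375 to 500 mg/m². These days assume no delays. The +3-day rituximab window does not change which infusions fall inside the DLT period.

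**4. What else might catch it?**

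- Within the DLT period, a grade ≥3 mucocutaneous reaction is not among the listed DLT exceptions, so the Data Review Team would see it.
- The Medical Monitor reviews all SAEs (Section 7.1.2.7), and this is not limited to the DLT period.
- Section 4.10.1 requires treatment to stop when the investigator judges the risk unacceptable.
- The Section 8.4 stopping criteria are not met by a single non-fatal, non-neurologic reaction. The SAE criterion needs more than one patient, and the criterion for AEs above grade 3 needs more than two.

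None of these says which text governs rituximab.

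**The case against.** The strongest reply is that the texts can be read together. Table 6 is general guidance on ending a hold, and its parent paragraph is permissive about resuming. Section 5.3.4.2 is specific to drug and event, is unconditional and speaks directly to re-administration. A drug discontinued under it is no longer on hold. The protocol also appears to work this way elsewhere. Table 6 only asks sites to consider reducing APR-246, while Tables 10 and 11 require permanent discontinuation for grade 4 creatinine, bilirubin, transaminase, infusion-reaction and CNS events, again with no pointer. If a missing pointer let Table 6 override Section 5.3, it would override those stops too.

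Much of this stands. The specific-over-general reading is plausible, a careful investigator would probably stop, and the missing pointer is not peculiar to rituximab. What remains is that the reading is written nowhere, while the rituximab cell goes further than the APR-246 cells: it tells the site to resume and names a single exception.

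Two stronger readings should be resisted. A reader might infer that the mucocutaneous reaction is the only event affected. Sections 5.3.4.5 and 5.3.4.1 do not allow that, since both cover non-infectious events and can call for stopping. A reader might also treat the counts of remaining infusions as a measure of risk. They show only when planned doses fall.

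**Conclusion.** The inconsistency is real and worth correcting. Read literally, Table 6 resumes rituximab at the same dose, or at a reduced dose on second occurrence, after a resolved grade 3–4 severe mucocutaneous reaction for which Section 5.3.4.2 orders discontinuation. The arrhythmia and infusion-reaction rules are less clear cases, so the mucocutaneous rule is the clearest conflict but is not shown to be the only one.

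The expected frequency is low. The documents give no event rate, so no number of patients can be stated. Re-exposure would require a reaction graded 3 or 4 (Section 5.3.4.2 does not grade severe), resolution to baseline or grade ≤1, a further scheduled infusion, and a site that follows the table over the specific section. The documents do not support saying that the protocol intends re-exposure or that sites would probably carry it out. No sample size, error rate or analysis is affected.

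**What to change.** In the first- and second-occurrence rituximab cells of Table 6, replace the infection-only exception with:

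> except serious infection or an event for which Section 5.3.4 requires discontinuation (e.g., severe mucocutaneous reaction), for which rituximab is permanently discontinued; Section 5.3.4 takes precedence over this table for rituximab.

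In the same edit, Section 5.3.4.5 should say whether it means the current infusion or all further rituximab, so that the new clause does not inherit that ambiguity.

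The cost is one clause in two cells and a few words in Section 5.3.4.5, with no extra patients, visits or procedures. The change does not address the similar missing pointer for APR-246, which would need its own line.

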5.3.2 APR-246

This section outlines the requirements for proceeding with treatment with APR-246, and the protocol rules for APR-246 dose modification due to management of QTc prolongation, CNS related AEs, nausea and vomiting, and infections.

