^a During APR-246 monotherapy lead-in, ECG should be collected in triplicate within 30 minutes prior to the infusion of APR-246 and within ±30 min of end of the 6-hour infusion (EOI) of APR-246 on Days 1 – 2. QTcF must be calculated from a mean of all three ECG readings.

If a patient starts treatment with a medication associated with QT interval prolongation, such as triazole antifungals, fluoroquinolones, and anti-emetics, while receiving study treatment, an additional pre- and post-dose (within 30 minutes prior to the infusion of APR-246 and within ±30 min of 6 hours after start of infusion) ECG should be performed on the next APR-246 treatment day.

5.3.2.4 Management Guidelines for APR-246 Dose Modifications and Criteria for Treatment Interruption and Re-Initiation with Treatment-Related Adverse Events

Table 10. Recommendations for APR-246 Dose Modifications and Criteria for Treatment Interruption and Re-Initiation with Treatment-Related Adverse Events

Renal Toxicities

Parameter	Worst toxicity ¹	Dose Modifications for APR-246
Serum Creatinine	Grade 1 (<1.5 × baseline)	Maintain dose level
	Grade 2 (>1.5-3.0 × baseline)	Omit dose until resolved to grade ≤1, then: If first occurrence, then maintain dose level If second or more consecutive occurrence, then ↓ 1 dose level
	Grade 3 (>3.0-6.0 × baseline)	Omit dose until resolved to grade ≤1, then: ↓ 1 dose level If not resolved or resolved in >7 days, evaluate if other contributing factors are present. If none, or after consideration of best interest of the patient, discontinue patient from APR-246. If other factors present, consider continuing after ↓ 1 dose level
	Grade 4 (>6.0 × baseline)	Permanently discontinue patient from APR-246

¹ Common Terminology Criteria for Adverse Events (CTCAE) version 5.

Hepatic Toxicities ¹

Parameter	Worst toxicity ²	Dose Modifications for APR-246
Bilirubin ³	Grade 1 (>ULN-1.5×ULN)	Maintain dose level with LFTs ⁴ monitored as per protocol
	Grade 2 (>1.5-3.0×ULN) with ALT or AST ≤3.0×ULN	Omit dose until resolved to grade ≤1, then: If resolved in ≤7 days, if first occurrence, then maintain dose level If second or more consecutive occurrence or if resolved in >7 days, then ↓ 1 dose level

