	Grade 3	
1st occurrence: Interrupt APR-246 dosing and monitor subject; treat promptly.
 
Resume at current dose level if toxicity resolves to grade ≤ 1 or baseline, with supportive care measures, within 72 hours of onset.
 
If toxicity does not resolve to grade ≤ 1 within 72 hours despite maximal medical intervention(s), then reduce APR-246 by 1 dose level once the toxicity resolves to grade ≤ 1 or baseline.
 
If unable to reduce APR-246 dose, discuss with study Medical Monitor before resuming or discontinuing APR-246.
 
For subsequent doses of APR-246, pre-medication with prophylactic supportive therapy should be given.
 
2nd occurrence: Interrupt APR-246 dosing and monitor subject; treat promptly.
 
Reduce APR-246 by 1 dose level if the toxicity resolves to grade ≤ 1 or baseline within 72 hours of onset.
 
If toxicity does not resolve to grade ≤ 1 despite maximal medical intervention(s) within 72 hours of onset, then consult with study Medical Monitor before resuming or discontinuing APR-246.
 
If unable to reduce APR-246 dose, discuss with study Medical Monitor before resuming or discontinuing treatment.
 
Prior to subsequent doses of APR-246, reassess prophylactic supportive therapy regimen and adjust as clinically indicated.
 
3rd occurrence: Interrupt APR-246 dosing and monitor subject; treat promptly. Consult with study Medical Monitor before resuming or discontinuing APR-246.

	Grade 4	Interrupt APR-246 dosing and monitor subject; treat promptly. Consult with study Medical Monitor to discuss dose modification or permanent discontinuation of APR-246.
Any Other Toxicity	Grade 3 or 4	
Delay dose until resolution to grade ≤ 1 or baseline, then $\downarrow 1$ dose level.
 
If unable to reduce APR-246 dose, discuss with study Medical Monitor before resuming or discontinuing APR-246.

¹ Common Terminology Criteria for Adverse Events (CTCAE) version 5.

Treating physicians should use clinical judgment and may consult the Medical Monitor for additional guidance with APR-246 dose modifications.

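### Table 6, 2nd occurrence, steps APR-246 down from the starting dose, so an already reduced patient gets no further step; and no visible text says whether Table 6 or Tables 10-11 governs related events

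*Combined protocol and SAP*

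**What the plan says.** Section 5.2 gives dose-management guidelines that "should be followed for each occurrence of a grade" 3 or higher hematologic toxicity (Table 5) or for non-hematologic toxicity (Table 6).

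- **Table 6, 1st occurrence:** hold, then consider reducing APR-246 "by one dose level from current dose for all future cycles of treatment if toxicity does not resolve to grade" 1 or lower within 7 days. If no reduction is possible, discuss with the Medical Monitor.
- **Table 6, 2nd occurrence:** hold, then "Consider reducing APR-246 by one dose level from starting dose for all future cycles of treatment". There is no 7-day condition and no fallback line for APR-246.
- **Table 5, 1st occurrence:** "Consider reducing APR-246 by one dose level from starting dose for all future cycles of treatment if toxicity does not resolve to grade" 1 or lower within 7 days.
- **Table 5, 2nd occurrence:** consider a reduction "by one dose level from current dose for all future cycles of treatment if the toxicity does not resolve" in that time. Both Table 5 rows have the fallback line.

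Section 5.3.2 introduces itself as outlining the requirements for proceeding with APR-246 and "the protocol rules for APR-246 dose modification due to management of QTc prolongation, CNS related AEs, nausea and vomiting, and infections". Within it, Table 10 offers recommendations for treatment-related events and Table 11 covers CNS events. At grade 4, the instruction for creatinine, bilirubin, AST/ALT, infusion reactions (Table 10) and CNS events (Table 11) is "Permanently discontinue patient from APR-246". For any other grade 3 or 4 toxicity, Table 10 says "Delay dose until resolution to grade" 1 or lower, or baseline, and then go down one level.

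**The concern.** A rule for a repeated severe toxicity should lower the dose step by step. Anchoring the 2nd step to the starting dose does that only while the patient is still on the starting dose. Once the patient has been reduced, or escalated as Section 4.1 allows after at least 3 cycles, the row can name the dose already being given, a dose two levels lower, or no dose at all. Table 5's reverse order suggests that the two words were transposed in Table 6.

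The second issue is that one related event can fall under two tables with different actions. Two patients with the same grade 4 event could be handled differently: one stopped for good, the other eligible to resume. For a few grade 3 events the choice of table could also decide whether a reduction occurs. Section 5.1.4 treats a toxicity-driven reduction as a DLT unless it is clearly and solely due to the disease.

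**Working it through.** **Dose ladder.** Table 3 has three levels: 1.5, 3.0 and 4.0 g/day. None is defined below 1.5 g. The row as written gives starting level minus one; the alternative is current level minus one. The cut is 1 − (new dose / current dose).

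| Start | Dose at 2nd event | Path | As written | From current dose |
|---|---|---|---|---|
| 4.0 g | 4.0 g | 1st event settled in time | 3.0 g; 1 − 3.0/4.0 = 25% | 3.0 g; 25% |
| 4.0 g | 3.0 g | reduced at 1st event | 3.0 g; 1 − 3.0/3.0 = 0% | 1.5 g; 1 − 1.5/3.0 = 50% |
| 3.0 g | 1.5 g | reduced at 1st event | 1.5 g; 0% | none defined |
| 3.0 g | 4.0 g | escalated, no reduction yet | 1.5 g; 1 − 1.5/4.0 = 62.5% | 3.0 g; 25% |
| 3.0 g | 3.0 g | escalated, then reduced | 1.5 g; 50% | 1.5 g; 50% |
| 1.5 g | 3.0 g | escalated, no reduction yet | none defined | 1.5 g; 50% |

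The row therefore works for a patient still on the starting dose and, by coincidence, for one escalated from 3.0 g and then brought back. It fails in the other four cases. For a patient reduced from 3.0 to 1.5 g, correcting the word alone is not enough, because no lower level exists; the fallback line is needed too. A further sequence shows that the wording is a slip. A Table 5 1st event (4.0 to 3.0 g) followed by a Table 6 1st event (3.0 to 1.5 g) leaves the Table 6 2nd-event row naming 3.0 g, above the current dose.

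**Tables side by side, for a treatment-related event.**

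| Event | Table 6 | Tables 10-11 |
|---|---|---|
| Grade 4 creatinine, bilirubin, AST/ALT, infusion reaction, CNS (5 types) | hold; consider a reduction | permanent stop |
| Grade 3 creatinine; grade 3 bilirubin with ALT or AST ≤3×ULN; any other grade 3-4 toxicity; 1st event, settled within 7 days | no directed reduction | one level down (for bilirubin, re-escalation may be considered) |
| Grade 3 nausea, vomiting or diarrhea, 1st event | 7-day trigger | 72-hour trigger |
| Grade 3 AST/ALT, 1st event, settled within 7 days | no directed reduction | maintain dose (agrees) |

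Table 11 also overlaps itself. Its row for grade 3 and above allows the infusion to resume if the event settles within 2 hours, and that label includes grade 4. The next row stops grade 4 permanently.

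**Ranking.** The 5.3.2 sentence lists QTc prolongation, CNS events, nausea and vomiting, and infections. It does not list renal, hepatic or infusion-reaction events. Section 5.3.3.1, on venetoclax, refers readers to Section 5.2 for overlapping toxicities. Neither ranks Table 6 against Tables 10-11. Section 5.1.1 is redacted and cannot be checked.

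**DLT counts.**

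1. Every non-hematologic exception in 5.1.4 is for grade 3. A grade 4 event is a DLT under either table unless clearly and solely due to disease.
2. Grade 3 bilirubin has no exception, so its count does not change either.
3. The excepted grade 3 events can differ. Take a related grade 3 infection at Dose Level 2 or 3, without grade 3-4 hematologic toxicity (which would move it to Table 5), that responds to treatment and settles by day 7. Table 10's residual row reduces the dose, which 5.1.4 makes a DLT; Table 6 directs no reduction.
4. Under the 3 + 3 rules in Section 4.1, one such event at Dose Level 2 changes 0/3 (advance) to 1/3 (add 3 patients). At Dose Level 2 or 3 it changes 1/6 (tolerated) to 2/6 (prior level becomes the maximum tolerated dose, MTD). No event rate is assumed.
5. For gastrointestinal events the same holds only if one still unresolved at 72 hours counts as responsive to supportive therapy.
6. The starting-dose clause does not itself alter the counts. A patient in the no-step case has already had a toxicity-driven reduction, and escalation comes after at least 3 cycles, when the DLT period has ended.

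**The case against.** The best defense is that none of this binds. Table 6 contains guidelines and says *consider*; Table 10 contains recommendations and is followed by a clinical-judgment clause; a 3rd event goes to the Medical Monitor; and Section 4.10.1 stops treatment when the Investigator judges the risk unacceptable. Table 6 is general guidance for three drugs, while Table 10 is specific to APR-246 and related events, so a site could sensibly let the specific table prevail. Following Table 10 breaches nothing in Table 6, which is silent, not contrary, on events settled within 7 days. All of this limits the harm. It does not supply a default, and it does not explain the reversed wording.

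A second objection is that if Table 10 governs related events, the Table 6 edit mainly affects unrelated ones and could deepen cuts for toxicity not attributed to treatment. The reach of the edit would indeed be narrow, but the row would remain inconsistent, and *consider* still lets the Investigator decline.

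A reader might infer more than the documents support:

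- That the grade 4 conflict shifts DLT counts or the MTD. It cannot, because no grade 4 non-hematologic event is excepted.
- That Section 5.3.2 claims authority over all APR-246 dosing. Its sentence names four areas, and four of the five grade 4 event types fall outside them.
- That the tables conflict throughout. The grade 3 AST/ALT case agrees.

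**Conclusion.** The point holds in two limited parts. First, the 2nd-occurrence row of Table 6 is misworded. Read literally it gives a 0% cut to a patient reduced from 4.0 to 3.0 g, a two-level drop to a patient escalated from 3.0 to 4.0 g and not yet reduced, and no defined dose to a patient escalated from 1.5 g. This rests only on the text and the Table 3 ladder. Second, Table 6 and Tables 10-11 give different actions for some of the same related events, and the visible text does not say which applies; the redacted section might. For the five grade 4 event types the consequence is inconsistent rechallenge. An effect on DLT counts is confined to excepted grade 3 events, depends on the Investigator's choice of table, and passes through DRT review. It is a minor correction, but one worth making.

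**What to change.** 1. In Table 6, 2nd occurrence, replace *starting* with *current*, and add the Medical Monitor fallback line that the 1st-occurrence row already has.
2. State in Section 5.2 that Tables 10 and 11 govern APR-246 dosing for treatment-related events and that Table 6 governs the rest.
3. Relabel Table 11's row for grade 3 and above as grade 3, so that the grade 4 stop is unambiguous.
4. State in Section 5.1.4 whether a protocol-directed reduction for an excepted grade 3 event counts as a DLT.

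The cost is one word, one line, one row label and two sentences in an amendment. No new data, visits or patients are needed.
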